1.3.2 Criteria for the selection of subjects

Inclusion criteria include:

- English proficiency
- 18 years of age or older
- Gestational age 14 weeks 0 days to 19 weeks 6 days
- Ability to provide informed consent
- Desire to proceed with outpatient D&E under moderate sedation

Exclusion criteria include:

- Contraindications to outpatient abortion or moderate sedation
- Current use of gabapentin (Neurontin®) or pregabalin (Lyrica®)
- Severe renal disease, per patient report
- Allergy or sensitivity to gabapentin or pregabalin

1.3.3 Subject recruitment and allocation

A total of 130 participants will be recruited from two sites at the time of abortion provision: MedStar Washington Hospital Center Family Planning and Preventative Care (MWHC) and Planned Parenthood of Metropolitan Washington DC (PPMW). PPMW has a diverse patient population, with a

majority of women being African American and age 20-29 years old. We will recruit from the PPMW clinic on the day they provide second trimester termination procedures. MWHC patients are generally referred from their general obstetrician’s office or self-referred for abortion and are seen in a private outpatient office. We will recruit eligible patients on days when we are not recruiting at PPMW. Baseline characteristics of the outpatient center at WHC and at PPMW in 2012 are shown below:

Table 2: Patient demographics

Age (years)	WHC	PPMW
<20	4%	12%
20-24	11%	38%
25-29	11%	25%
30-39	68%	21%
40 or more	6%	5%
Race		
Black, non-Hispanic	22%	65%
White, non-Hispanic	61%	16%
Hispanic	11%	8%
Multiracial	0%	8%
Other/unknown	6%	3%

In both recruitment settings, D&E is offered as a same-day procedure under moderate sedation with fentanyl and midazolam. Standard care at both sites includes cervical preparation with misoprostol and/or osmotic dilators, initiated at least two hours prior to D&E. Patients will be recruited after gestational age is confirmed to be 14 through 19 weeks, after eligibility for moderate sedation is confirmed, and after patients have provided informed consent for surgical abortion (Appendix A). This occurs after the patient has completed ultrasound, counseling, lab studies, and documentation of medical history. Patients will generally be recruited after initiation of cervical preparation, as this is a time when clinic flow will not be disrupted by study recruitment. Some participants may be recruited before cervical preparation initiation, as clinic flow permits, but no participant will receive study medications until after cervical preparation has begun.

Patients will be approached by study staff in a private room where eligibility will be assessed and consent will be obtained. A detailed explanation of the study will be provided and written informed consent will be obtained (Appendix B). The patient will be given a copy of her signed informed consent. After the consent is signed, eligibility for the study will be confirmed. Enrollment will be limited to 4 participants per site per day to minimize the impact on clinic flow. Permission to conduct this study has been obtained from the medical directors at both sites and will be approved by Planned Parenthood Federation of America research committee as well as the MHRI IRB.

A MHRI statistician not involved in the conduct of the study will produce the allocation sequence using a computer generated random sequence. The MedStar Health Research Pharmacy will prepare sequentially numbered sealed opaque allocation packets containing the appropriate study medications within opaque capsules. The packets will not be assigned to a participant until eligibility is confirmed. Randomization assignment will only be revealed at the point of data analysis, serious adverse event, or if interim assessment is needed.

1.3.4 Description of the drugs and devices to be studied

Gabapentin (Neurontin®) is FDA-approved for the treatment of post-herpetic neuralgia and seizure disorder. Off-label uses include chronic refractory cough, neuropathy, hot flashes, restless leg syndrome, social anxiety disorder, and post-operative pain. Although its chemical structure is similar to GABA and it was originally suspected to be a GABA analog, the primary mechanism of action is suspected to be via central nervous system voltage-gated calcium channels and the inhibition of excitatory neurotransmitter release [21]. In the U.S., it is available as 100 mg, 300 mg, and 400 mg capsules or 600 mg or 800 mg tablets and is intended for oral consumption. Although originally brought to market as Neurontin® by Pfizer, gabapentin is now available as a generic from multiple pharmaceutical companies. A single 600 mg tablet costs less than \$5 wholesale. Oral consumption leads to a peak serum concentration in 2-4 hours with a half-life of 5-8 hours [5].

Gabapentin has an impressive safety record. It is metabolized renally and should be dose-adjusted for renal impairment [5]. Drug interactions are uncommon but include decreased absorption when consumed with antacids [5]. The most commonly reported side effects include dizziness, somnolence, ataxia, and edema and are more pronounced with chronic use and dose ≥ 1200 mg [22]. Adverse events are uncommon and include seizure or worsening depression at the time of chronic gabapentin use cessation [5]. Recently, concerns regarding respiratory depression have been raised due

to one retrospective review [23]. In this study, most patients were greater than 50 years old and the average length of surgery was 3 hours. Patients who received gabapentin were slightly more likely to have respiratory depression in recovery (17.5% vs 15.8%, $p=0.11$). It was only with multivariate analysis that a statistically significant difference was noted. Given the methods, this finding may reflect uncontrolled bias, possibly resulting from anesthesiologists giving gabapentin to patients most at risk of respiratory events to reduce narcotic need. Characteristics associated with respiratory depression after gabapentin use were being elderly, underlying conditions that affect breathing, and concurrent use with opioids [23]. The results of this study contradict a large meta-analysis which showed increased sedation but no increase in respiratory depression with pre-operative gabapentin [10].

1.3.5 Admission procedure

After eligibility has been confirmed and informed consent has been obtained, participants will complete a questionnaire assessing demographic information and medical history (Appendix C). Relevant baseline characteristics including age, gravidity, parity, race, ethnicity, and weeks of gestation will be collected. We will also document pre-existing psychiatric disorders such as depression, anxiety, bipolar disorder and chronic pain syndromes.

She will then be assigned to the next sequentially numbered randomization packet. After initiation of cervical preparation, the participant will consume the study drug from the packet with water or clear juice. Time of administration will be recorded on the patient's chart and will occur at least one hour before the planned procedure. All medications given throughout the clinic experience will be recorded. Method(s) of cervical preparation will be recorded. Antibiotic, anti-emetic, and analgesic administration will be standardized but medications may be adjusted to the need of each woman to accommodate patient characteristics such as allergies and without regard to her enrollment in this study.

1.3.6 Follow-up procedure

The pre-operative assessment will be completed by the study coordinator immediately prior to initiation of moderate sedation (Appendix D), which usually occurs in the procedure room. The intra-operative assessments will be administered by the study coordinator during the procedure at the specified time or point during the procedure (Appendix E). The times of all assessments will be noted. The time of speculum removal will be considered the time of procedure completion.

A same-day post-operative assessment will be completed by the participant 30 minutes (20-40 min range) after procedure completion in the recovery room (Appendix F). After completion of the post-operative assessment patients will receive a \$40 gift card and be reminded that they will receive a phone call the following day.

A phone call will be made to all participants on the day following their procedure to administer the POD1 assessment (Appendix G). The participant phone number will be tested at the time of enrollment and three attempts will be made to reach participants by phone on POD1. Participants will be provided with a phone number for the study coordinator should they have trouble receiving phone calls. Patients that complete the POD1 assessment will be mailed a \$10 gift card.

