Appendix F: Post-operative assessments [40](#)

Appendix G: Post-operative day 1 assessment [42](#)

Deleted: 39

Deleted: 41

PROJECT SUMMARY

Justification.

Over 900,000 abortion procedures are performed annually in the United States [1]. For many women, pain relief during abortion is inadequate despite the use of non-steroidal anti-inflammatory drugs, local anesthetics, opioids, and/or moderate sedation. Research on pain control during abortion has focused on methods for relief during first-trimester suction curettage with little research dedicated to pain during dilation and evacuation (D&E). Gabapentin (Neurontin®) has emerged as an effective adjunct to pain management for a variety of surgical procedures. Gabapentin is inexpensive and is also effective in reducing anxiety, nausea, and vomiting. The addition of pre-operative gabapentin to moderate sedation during D&E may lead to increased patient satisfaction and pain relief without significantly increasing risk or cost.

Proposed Research.

We propose a randomized controlled double-blinded trial evaluating the use of adjunct gabapentin versus placebo in addition to moderate sedation during D&E. We hypothesize that 600 mg oral gabapentin administered pre-operatively at the time of cervical preparation initiation will improve intra-operative pain control. We also hypothesize that it will improve pre- and post-operative pain, anxiety, nausea, vomiting, and overall satisfaction with pain management during D&E. We hypothesize that the doses of moderate sedation agents required to obtain adequate sedation will be decreased in patients receiving gabapentin versus placebo. We also plan to compare the risk of adverse events with adjunct gabapentin versus placebo with moderate sedation.

To test our hypotheses we plan to enroll 130 participants who will be randomized 1:1 to receive either 600 mg gabapentin or placebo at the initiation of cervical preparation. Baseline participant characteristics will be recorded. Pain will be assessed pre-operatively, at 3 intraoperative time points, and postoperatively by 100 mm visual analog scale (VAS). We plan to assess satisfaction with pain control, nausea, vomiting, and anxiety preoperatively and post-operatively, using 5-point Likert scales and the State Trait Anxiety Inventory, respectively. A final assessment will be made by phone on post-operative day one to evaluate overall satisfaction and perform a final screen for adverse events.

New features.

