1.3 Design and methodology

1.3.1 Research design and General Methodological Approach

We propose a randomized controlled double-blinded trial comparing oral gabapentin 600 mg to placebo among patients undergoing outpatient same-day dilation and evacuation under moderate sedation. We propose to give the study drug (gabapentin or placebo) shortly after the initiation of same-day cervical preparation and a minimum of one hour prior to D&E. The primary study outcome is maximum pain during D&E as recorded by 100-mm VAS (Table 1). Secondary outcomes include total doses of IV sedation, pain at three time points during D&E, perioperative pain, anxiety, nausea, vomiting, patient satisfaction with pain management, oxygen saturation during moderate sedation, and administration of sedation reversal agents. We will also contact patients by phone on post-operative day 1 (POD1) to assess for prolonged or delayed side effects, adverse events and overall satisfaction with pain control.

Study medications will be administered by study staff, Planned Parenthood of Metropolitan Washington DC (PPMW) staff, or MedStar Washington Hospital Center (MWHC) staff after initiation of cervical preparation. The MedStar Health Research Institute (MHRI) pharmacy will prepare identical capsules containing gabapentin 600 mg or methylcellulose placebo. The pharmacy will package the capsules in sequentially numbered opaque sealed envelopes according to a computer-generated 1:1 randomization scheme prepared by MHRI. Study staff involved in administering medications and assessing outcomes, clinical staff (health care associates, nurses, physicians), and participants will be blinded to randomization assignment. Randomization assignment will only be revealed at the time of data analysis or in the case of a serious adverse event. As there is no standard or optimal dose of pre-operative gabapentin, we have chosen to use a dose of 600 mg with the aim of maximizing pain relief while minimizing the sedative effect. This is the same dose currently being investigated during first-trimester abortion at Emory University.

Administration of analgesics, anesthetics, and anti-emetics will be standardized. Patients will generally receive the following oral pre-procedure regimen: naproxen 500 mg, ~~tramadol 50 mg,~~

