1.3.7 Criteria for discontinuation

Participants may withdraw at any time by refusing to participate in further assessments or by electing not to continue with pregnancy termination.

We expect loss to follow up for all primary and most secondary outcomes to be rare as most assessments are made on the date of study enrollment. We expect some loss to follow up for the POD1 assessment but will take the following steps to minimize this loss: testing of participant phone numbers at the time of enrollment, providing a reminder about the phone call prior to clinic discharge, agreeing in advance on a convenient time for the follow up phone call, providing participants with the study coordinators phone number, and provision of a gift card by mail after completion.

Patients who experience serious adverse events will be discontinued from the study and allocation may be revealed to ensure appropriate management of medical conditions. An adverse event (AE) is defined as any health-related reaction, effect, toxicity or abnormal laboratory result that a study participant experiences during the course of the study, irrespective of relationship to the study intervention. A serious adverse event (SAE) is defined as any experience that is fatal or life threatening, requires in-patient hospitalization or prolongation of an existing hospitalization, or results in a persistent or significant disability or incapacity.

A data safety monitoring board (DSMB) will be assembled. A DSMB meeting will be triggered by a case of respiratory compromise requiring sedation reversal (naloxone or flumazenil). This board will consist of clinicians and researchers knowledgeable in abortion care, moderate sedation, and gabapentin. The following individuals have agreed to serve on the DSMB:

- [name], Professor of Obstetrics and Gynecology, Division Director of Family Planning, University of California Davis

- [name], MPH, Senior Director of Medical Services, PPFA
- [name], PhD, Professor of Anesthesia/Dean, University of California San Francisco

If triggered to meet, they will review the cumulative data to date and provide advice regarding the safety of continuing, modifying, or discontinuing the study.

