1.6 Main problems anticipated

The frequency of intraoperative pain assessments will require the study coordinator to remain in the room throughout the procedure and therefore we will limit recruitment to 4 patients per day per site to minimize disruptions to clinic flow. This will also reduce the chance of missing data from

perioperative assessments as a result of the coordinator's unavailability. We also anticipate some loss to follow up at the time of the POD1 assessment; this assessment is a secondary outcome and we are taking steps to minimize loss as described in section 1.3.6. Our final concern relates to the potential for over-sedation with the combination of gabapentin and opioids, which could impact both patient safety and clinic flow if discharge is delayed. Although dose-finding studies have not identified an ideal dose, we suspect that a one-time dose of 600 mg will improve pain control without significantly contributing to sedation. Sedation reversal agents are available at both sites. Adverse events, including respiratory depression, will be monitored, reviewed, and allocation revealed if necessary.

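### The final adverse-event screen rests on three calls in one day, and no active follow-up is described for women not reached

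*Combined protocol and SAP*

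**What the plan says.** The Project Summary (Proposed Research) gives the POD1 call two purposes: "A final assessment will be made by phone on post-operative day one to evaluate overall satisfaction and perform a final screen for adverse events". Section 1.3.1 says that the call is made "to assess for prolonged or delayed side effects, adverse events and overall satisfaction with pain control". The last scheduled assessment before it is the recovery-room form, 20-40 minutes after speculum removal (section 1.3.6, Table 1). No contact is scheduled after POD1.

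On reaching participants, section 1.3.6 says that "three attempts will be made to reach participants by phone on POD1". It adds: "Participants will be provided with a phone number for the study coordinator should they have trouble receiving phone calls".

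The plan expects losses. Section 1.3.7 says "We expect some loss to follow up for the POD1 assessment", and section 1.6 says "We also anticipate some loss to follow up at the time of the POD1 assessment". Section 1.3.7 lists five measures against this: testing the phone number, a reminder before discharge, "agreeing in advance on a convenient time for the follow up phone call", giving out the coordinator's number, and a mailed gift card.

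Section 1.3.7 also counts in-patient hospitalization as a serious adverse event and has a co-investigator review all adverse events. Objective 4 (section 1.1.2) compares adverse events between arms, with the hypothesis that gabapentin does not increase them. Section 1.3.10 names an intention-to-treat analysis but does not say how women without a POD1 assessment enter that comparison.

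**The concern.** The call is the only scheduled route to events after discharge, yet every attempt falls on one calendar day. All five retention measures aim at making the POD1 call succeed. None says what happens if it fails.

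The reason for non-contact matters. A woman who has been admitted, or who feels too ill to answer, is plausibly among those not reached. If so, the missing reports are not a random subset. Leaving these women out of the denominator, or counting them as event-free, would both make delayed harm look rarer than it was. Because the Objective 4 hypothesis is one of no increase, incomplete ascertainment leans towards confirming it.

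**Working it through.** **No plan figure to reproduce.** The documents give no expected POD1 loss. The only derived design figure is the sample size, which reproduces: 2 × (1.960 + 0.842)² × 25² / 13² ≈ 58.1, rounded up to 59 per arm (two-sided 0.05, 80% power, SD 25, difference 13; section 1.3.11). The margin from 118 to 130 is 1 − 118/130 = 9.2%. It covers withdrawals and incomplete data for the primary outcome, so it is not a POD1 loss rate. Maximum pain is recorded 3-5 minutes after speculum removal, so this point does not touch it.

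**What remains for a woman who misses three calls.**
- Later call or alternate contact: none described in sections 1.3.6, 1.3.7 or 1.6.
- Record check: the review in Appendix C covers clinic-day items (gestational age, medications, cervical preparation, sedation, reversal). It has no item for events after discharge.
- Participant-initiated contact: possible through the coordinator's number, which is offered for trouble receiving calls.
- Event known to a site: would be reviewed under section 1.3.7, but reviewing events does not find them.

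**Number affected (non-contact rates assumed).** Unreached = 130 × d. For d = 10%, 20%, 30%: 13, 26, 39 women.

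**Loss of precision alone.** If no event is reported among m women reached, the one-sided 95% upper bound on the event rate is 1 − 0.05^(1/m).
- m = 130: 2.3%
- m = 117: 2.5%
- m = 104: 2.8%
- m = 91: 3.2%

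This effect is small.

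**Possible bias (illustration; all rates assumed).** Take delayed events that only the call would reveal, with true rate p = 5%. Let women with an event be r times as likely to be unreached. With overall non-contact d, the share of events missed is e = r × d / (1 − p + p × r). The observed rate is p(1 − e)/(1 − d) if unreached women are dropped, and p(1 − e) if they are counted as event-free.

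| d | r | Events missed | Rate if dropped | Rate if counted event-free |
|---|---|---|---|---|
| 10% | 1 | 10% | 5.0% | 4.5% |
| 20% | 1 | 20% | 5.0% | 4.0% |
| 30% | 1 | 30% | 5.0% | 3.5% |
| 10% | 3 | 27% | 4.0% | 3.6% |
| 20% | 3 | 55% | 2.8% | 2.3% |
| 30% | 3 | 82% | 1.3% | 0.9% |

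Dropping unreached women is harmless to the rate only when r = 1. Counting them as event-free understates it in every row.

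**Would a later call still be useful?** With the half-life of 5-8 hours in section 1.3.4, the fraction remaining is 0.5^(t/half-life): 3.6% to 12.5% at 24 hours and 0.1% to 1.6% at 48 hours. A call on POD2 or POD3 can therefore ask about nearly the whole exposure. Appendix G item 9, however, refers only to the day of the call and the day before. Asked unchanged on POD2 or POD3, it would leave out the procedure day.

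**The case against.** A reader might infer that an unreached woman has no post-discharge safety data at all. The documents do not support that. She holds the coordinator's number, and a co-investigator reviews all adverse events, so a call-in or an event known to a site could be captured. The consent form and a few other parts were not in the text supplied and may tell women how to report problems. What stands is narrower: those routes are passive, and no active one is described.

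A reader might also infer that observation ends with the 20-40 minute form. It does not. Section 1.3.1 monitors respiratory depression, reversal and hospital transfer; section 1.3.5 records all medications given during the clinic stay; Appendix F records the time of discharge.

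Nor does it follow that the period around peak concentration goes unobserved. Section 1.3.4 puts the peak at 2-4 hours. At the one-hour dosing minimum, the form falls 80-100 minutes plus the procedure time after dosing, which can precede the peak. Dosing about two hours before D&E puts it at 140-160 minutes plus the procedure time, at or beyond the start of that window. Section 1.3.1 has the drug given shortly after cervical preparation begins, and section 1.3.3 has preparation begin at least two hours before D&E. The early case is therefore a limiting one.

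Finally, it is fair to say that the main sedation measures are taken on site, that the plan openly expects POD1 loss and takes five steps against it, and that section 1.3.12 concedes limited ability to detect rare complications. A link between non-contact and harm is plausible but not shown. All this keeps the point modest. It does not supply the missing rule for women who are not reached.

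**Conclusion.** The point holds as a gap in ascertainment. All attempts at the plan's final adverse-event screen are confined to POD1, and the text supplied describes no active post-discharge safety ascertainment for women not reached. At assumed non-contact of 10%, 20% or 30%, 13, 26 or 39 of 130 women would have no POD1 screen.

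Whether Objective 4 would be biased depends on two things the documents do not settle: whether non-contact is related to events, and whether unreached women are dropped or counted as event-free. If non-contact is unrelated and they are dropped, the rate is unbiased and the cost is a little precision. If it is related, delayed events are understated; the tabulated sizes rest wholly on assumed rates.

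This is a cheap improvement, not a flaw in the trial's main comparison.

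**What to change.** - **Section 1.3.6:** keep POD1 as the target day. If the three calls fail, continue daily attempts through POD3. The Appendix G header already has date and time fields, so late responders can be flagged without a new field.
- **Appendix G, item 9:** ask about complications or side effects *since your procedure*. This covers the procedure day whenever the call succeeds and keeps the interval between the recovery form and discharge.
- **Women still unreached:** check the two sites' own records for return, transfer or admission. Admissions elsewhere may be missed, so an empty record is not proof of no event.
- **Section 1.3.10:** report the number without post-discharge contact by arm, and do not count these women as event-free.

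The cost is a few extra calls and record checks by the existing coordinator for the minority not reached, and slightly longer recall for late responders, whose satisfaction scores can be flagged by day. The primary outcome and sample size do not change.
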